We have made pragmatic choices, aiming to investigate the outcomes set out in the logic model while minimising burden on local authorities and participants, and maximising data quality and completeness. We have chosen to contact families using an online survey at baseline and endline, with carers without valid email addresses sent a copy by post, and reminders sent by email, post and text message as appropriate. The survey will be sent to all carers in the trial. As shown in the table below, we have scheduled prompt text messages for the baseline and endline survey, and reminder text messages for non-responders to the endline survey. We plan to keep the survey open for one month, but may extend this deadline depending on the response rate.

The baseline survey will be sent to carers shortly after families have been randomised. We therefore anticipate that most surveys will be sent in March 2023 as this is when most families will enter the programme i.e. when local authorities share contact details with Barnardo's to invite families to information sessions. However, where families become eligible or interested throughout the trial period, the survey will be sent on a rolling basis following randomisation. The endline survey will be sent in July 2024, once all WRAP Level 1 delivery has ended. This is so that the endline survey can theoretically capture any change, or lack of change, that has occurred by both adults and children/young people attending Level 1 WRAP. We anticipate that capturing outcomes at endline will pose challenges for retention and have therefore made the following plans to boost the response rate:

¹⁶ Bulus M, Dong N, Kelcey B, Spybrook J (2021). *PowerUpR: Power Analysis Tools for Multilevel Randomized Experiments*. R package version 1.1.0, <https://CRAN.R-project.org/package=PowerUpR>.

1. Foster carers and kinship carers will receive a £10 voucher upon completion of the survey at baseline and another £10 voucher at endline.
2. We will send a reminder text and email ahead of the endline survey (June 2024) to remind foster and kinship carers that they will receive the survey in July 2024.
3. We will consider phoning all randomised foster carers and kinship carers at midpoint as a courtesy to check on engagement and remind them of the endline survey. However, we will weigh this up against whether this will be too much contact and considered a nuisance.

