4. We will work with Barnardo's to explore mechanisms for reminding participants of the endline survey, including social media, via fostering social workers, and at the Keeping Connected groups.
5. We will check whether contact details for participants are up-to-date with local authority records.

In order to minimise data storage and use the most up-to-date contact details, we will obtain contact details for all randomised carers from the Barnardo's Expression of Interest form.

Table 3. Milestones for outcome measure collection

Task	Date
Referrals of families sent by Barnardo's to Coram	March-April 2023
Eligible referred families randomised by Coram, then randomisation outcomes shared with local authorities and Barnardo's	March – April 2023
Coram emails/posts baseline survey to carers (with prompt text message, if mobile phone number available)	March – April 2023
Coram randomises eligible referred families, then emails/posts baseline surveys to carers (with prompt text message, if possible)	March 2023 – March 2024
Coram sends endline survey by email/post to carers (with prompt text message, if mobile phone number available)	1 st July 2024
Coram requests administrative data from local authorities	1 st July 2024
Coram sends reminder email/text message/post to non-respondent carers	July 2024
Deadline for local authorities to send Coram administrative data request Deadline for carers to complete endline survey	31 st July 2024

The online baseline and endline surveys are hosted on Smart Survey. The prompt text message will read:

'Hi, we're Coram. You may remember agreeing to take part in our study of families in Hull and Lincolnshire. Today we emailed you a survey about your experiences as a carer: [link]. Please complete by 30th April. We will send you a £10 voucher if you complete this survey, and we will also send you another £10 voucher if you complete an additional survey in July 2024.'

The reminder text for the endline survey will read:

'Last chance to have your say! We have emailed you a survey about your experiences as a carer. Your response will help Barnardo's and local authorities to offer the best possible wellbeing support to the fostering community. We will send you a £10 voucher if you complete this survey by 31st July. The link to the survey is [link]'

We will also consider including an additional prize draw in a reminder text, dependent on the response rate.

Type	Outcome	Outcome measure	Collected from	Baseline	Endline

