1. Has the foster carer ceased fostering? (yes, no)
2. Why has the foster carer ceased fostering? (resignation, uncontested termination of approval, contested termination of approval, other, unknown)
3. Other reason (if applicable)
4. Contributing factors (e.g. illness)

We will also seek data on referrals to Child and Adolescent Mental Health Services - **CAMHS referrals** - for foster children in the fostering household. From discussions with local authority data leads, it is likely that where this information is centrally stored, it will only be available for foster children in the household and not other children. This analysis will be exploratory only.

While not an outcome variable, we also intend to request data from Barnardo's on **engagement** with the intervention. This will include attendance at information sessions, the number of WRAP sessions attended and the dates of WRAP sessions. The intervention is designed to be self-sustaining, so we will also gather and match in data from Barnardo's on who leads the ongoing Keeping Connected groups. This will allow us to describe the delivery of the intervention in the final report and will be used in the compliance analysis.

Analysis plan

Does the intervention work?

Q1 Analysis

The trial will take an RCT design. The primary outcome will be collected at baseline (for most families, March 2023) and endline (for all families, July 2024). All outcomes will be analysed on an intention to treat basis in that all participants will be analysed according to the trial arm to which they were assigned, as opposed to the service they received.

Families are the unit of randomisation, but data will be analysed at the individual level e.g. individual foster child placement breakdown, individual foster carer turnover, and individual SDQ outcomes for foster children. We will need to account for clustering within our analysis. We may receive two responses from couples. In this case, we will use clustered standard errors to account for this.

We know from prior experience of analysing routinely collected Strengths and Difficulties scores for looked-after children that local authorities do not generally know or collect data on the version of the SDQ used and who completed it (carer, child, or social worker). We therefore anticipate it will be challenging to standardise scores on the SDQ by informant, but will do so if data allows.

Data cleaning

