For outcome data, we will compute missingness indicators for each of our outcomes and regress these indicators on covariates. If these are significant, then the data is not missing completely at random. We will also check whether the data is experimentally missing at random by regressing the missingness indicator on a treatment dummy. If this is not significant, we will use listwise deletion of observations without outcome data, but if this is significant we will use a last observation carried forward (LOCF) approach. For questionnaires such as the SDQ and the WEMWBS, we will prioritise the approach to missing data as specified in the measure guidance. For example, the user guide for the WEMWBS advises against imputing missing data for participants where more than three items are missing²¹.

We will use multiple imputation for our covariates and conduct our analyses and compare this with our analysis for only complete cases. We will then assess both outputs to determine how similar the treatment estimates are in terms of their significance and direction (20% range as rule of thumb). If these coefficients are not similar, we can reasonably conclude that these data are missing not at random. For these data, we will carry out multiple imputation for our main analysis, with accompanying sensitivity analysis to evaluate the assumptions used. If these coefficients are similar and covariate coefficients are not significant when regressed onto missingness indicators, we can conclude that these data are missing completely at random. If the coefficients are similar, but the covariate coefficients are significant we can assume that these data are missing at random. For missing covariates (unknown), we will use mean average imputation and report how this affects the results.

Criteria	Treatment estimates are similar for complete cases analysis and multiply imputed analysis	Treatment estimates are not similar for complete cases analysis and multiply imputed analysis
Covariates significant when regressed onto missingness indicators	Missing at random (MAR) Multiple imputation with accompanying sensitivity analysis Impute missing data to fix bias and for power	Missing not at random (MNAR) Multiple imputation with accompanying sensitivity analysis
Covariates not significant when regressed onto missingness indicators	Missing completely at random (MCAR)	Missing not at random (MNAR)

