²¹ Stewart-Brown, S., & Janmohamed, K. (2008). Warwick-Edinburgh mental well-being scale. User guide. Version, 1(10.1037).

	Impute missing data to fix standard errors and for power	Multiple imputation with accompanying sensitivity analysis
--	--	--

Descriptives

We will calculate and report descriptive statistics, including the characteristics of the intervention and control groups on each key variable collected. We will carry out balance checks to report on how balanced the characteristics of respondents are across treatment and control groups. If any characteristics are significantly unbalanced between trial arms, we will adjust these in our outcomes analysis.

We will report full baseline characteristics of the sample, the characteristics of those lost to follow-up, and the characteristics of the analysable sample. We will compare demographic characteristics of our recruited sample (those who consent) and analysable sample (those who complete the endline survey) in terms of representativeness of the population in the three local authorities. Where appropriate, we will report ICCs to describe the clustered nature of the data (e.g., SDQ scores for foster children in a family).

Primary outcome analysis

Our primary outcome is a numeric variable. We will use linear regression to estimate the average effect of the treatment allocation on this variable using a Huber-White (HW) robust error procedure to account for heteroscedasticity and clustering. We will include fixed effects for local authority. The coefficient will be an estimate of the size and direction of the treatment effect and its significance will be tested with a two-tailed 5% Type I error threshold. Following What Works for Children's Social Care statistical analysis guidance, we will report our effect sizes as Glass' delta using unconditional (unadjusted) standard deviations.

Our primary model will only include predictors that are significantly unbalanced between trial arms. We will consider the following variables for possible inclusion in the model in sensitivity analyses, and compare impact estimates of this model to the first model to assess the extent to which the further controls have increased or decreased the impact effect. This may give us further insights into relationships which can help to inform future work. We will decide whether to include them or not based on whether or not they significantly predict the primary outcome:

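### The missing-outcome rule lets a significance test choose the method and, when significant, carries the baseline forward, which shrinks any real effect and turns a common trend into an arm difference

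*Protocol*

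**What the plan says.** **Outcomes (Treatment of missing data).** For each outcome, an indicator of missingness is tested against trial arm, and the result picks the method. One branch reads: "If this is not significant, we will use listwise deletion of observations without outcome data". The other branch, for a test that does reach significance, switches to single imputation from the earlier wave: "but if this is significant we will use a last observation carried forward (LOCF) approach". The next sentence gives priority to each questionnaire's own guidance. Its example is the WEMWBS user guide, which advises against imputing when more than three items are missing. The Secondary outcomes analysis section adopts the same handling.

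**Waves (Outcome measures; Analysis plan).** The primary outcome is collected twice: at baseline, March 2023 for most families, and in July 2024. "The baseline survey will be sent to carers shortly after families have been randomised". The outcome table marks placement changes, carer turnover and CAMHS referrals as endline only.

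**Primary model (Primary outcome analysis).** "Our primary model will only include predictors that are significantly unbalanced between trial arms". Baseline WEMWBS is listed only as a candidate for sensitivity models.

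**Covariates (Treatment of missing data).** This is a separate step: "We will use multiple imputation for our covariates and conduct our analyses and compare this with our analysis for only complete cases". Similarity is judged by a 20% rule of thumb. "If these coefficients are not similar, we can reasonably conclude that these data are missing not at random". The same paragraph also assigns mean imputation to missing (unknown) covariates.

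**Reminders (Outcome measures).** The team will explore ways of reminding participants about the endline survey, "including social media, via fostering social workers, and at the Keeping Connected groups".

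**The concern.** About 30% of randomised adults are expected to have no primary outcome, so the handling of non-response matters to the main estimate. Four features look wrong.

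1. With two waves, LOCF is baseline carried forward. It assumes no change in non-responders and is invoked when non-response differs between arms. In that case any common trend enters the treatment contrast.
2. The method hangs on a test that may have little power, and a non-significant result does not show that missingness is ignorable. The fallback, listwise deletion, then runs in a model that leaves out baseline WEMWBS unless it happens to be significantly unbalanced.
3. LOCF has nothing to carry for carers who skip the post-randomisation baseline survey, or for the three administrative outcomes collected only at endline.
4. The covariate step labels data MNAR on evidence that cannot support the label, and it prescribes both multiple and mean imputation without saying which applies when.

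**Working it through.** **The plan's own figures.** Analysable adults: 335 × 0.98 (consent kept) × 0.95 (valid outcome) × 0.75 (response) = 233.9. Households: 178 × 0.69825 = 124.3. These match the stated 234 and 124, so the loss is 1 − 234/335 ≈ 30%. The Annex 2 inputs give an MDES of 0.368 (stated 0.37) and a standard error of about 0.37/2.8 = 0.13 SD.

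**LOCF expectation.** Let mT and mC be the proportions missing, d the common change and e the effect, all in SD. Non-responders contribute zero change, so the estimate has expectation (1 − mT)(d + e) − (1 − mC)d = (1 − mT)e + (mC − mT)d. The bias is −mT·e + (mC − mT)d. The protocol gives no arm-specific missingness and no trend, so both are assumed. The effect 0.24 is the pooled effect on self-perceived recovery in the Evidence base section.

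**Test power.** 168 adults per arm, two-sided 5%, before clustering.
- 25% v 35%: SE = √[(0.25×0.75 + 0.35×0.65)/168] = 0.0497; z = 2.01; power = Φ(0.05) ≈ 52%.
- 25% v 40%: SE = √[(0.25×0.75 + 0.40×0.60)/168] = 0.0504; z = 2.97; power ≈ 84%.
- 25% v 35% at design effect 1.9 (household members always respond or fail together): z = 2.01/√1.9 = 1.46; power about 0.3.

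| Missing, intervention v control | e = 0.24, d = −0.3 / 0 / +0.3 | e = 0, d = −0.3 / 0 / +0.3 | Test power |
|---|---|---|---|
| 25% v 35% | 0.15 / 0.18 / 0.21 | −0.03 / 0 / +0.03 | 52% |
| 25% v 40% | 0.135 / 0.18 / 0.225 | −0.045 / 0 / +0.045 | 84% |

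**Simulation.** 178 households, ICC 0.4, assumed baseline–endline correlation 0.775, 25% v 35% missing, true effect 0.37, d from −0.3 to +0.3, 800 runs per setting. Mean estimates:

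| Missingness | LOCF | Listwise, unadjusted | Listwise, baseline-adjusted |
|---|---|---|---|
| Completely random within arm | 0.245–0.307 | 0.368–0.373 | 0.370–0.372 |
| Depends on baseline | 0.254–0.314 | 0.321–0.325 | 0.370–0.371 |
| Depends on endline (MNAR) | 0.242–0.304 | 0.307–0.312 | 0.340–0.347 |

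With 30% missing in both arms and d = 0, unadjusted listwise deletion was biased by less than 0.01 under all three mechanisms. LOCF gave 0.254–0.261, against 0.70 × 0.37 = 0.259 by formula. LOCF was not worse everywhere: under MNAR with no effect and no trend its bias was −0.009, against −0.027 for the adjusted analysis.

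**The 20% rule.** n = 234, 25% of a covariate missing, 400 runs per setting. At effect 0.2, MNAR was declared in 27.5% of MCAR, 35.5% of MAR and 31.2% of truly MNAR data sets. At effect 0.37 the rates were 4.8%, 10.8% and 8.8%. The rule responds to effect size, not to mechanism.

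**The case against.** The strongest reply is that LOCF may never reach the primary outcome. The plan puts the measure guidance first, the WEMWBS guidance is against imputing beyond three missing items, and a non-responder lacks all 14. That reading is open. However, the example concerns missing items, the LOCF sentence covers every outcome, and the two are not reconciled. The ambiguity is itself part of the fault, and any multiple imputation of the outcome must answer the same sentence.

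Several stronger readings are tempting, and the documents do not support them.

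- *A reader might infer that the rule is biased exactly when it is triggered.* Listwise deletion is not biased as such, and LOCF is unbiased with no effect and no trend.
- *A reader might infer that the rule can set the sign of the result.* At 25% v 40%, reversing a true 0.24 needs 0.18 + 0.15d < 0, a common decline beyond 1.2 SD. The null bias of 0.045 is about a third of the 0.13 standard error.
- *A reader might combine the larger bias with the weaker test.* They belong to different scenarios, as the first table shows.
- *A reader might treat the MNAR table as part of the outcome rule.* It is worded for covariates, and the primary model contains few of them. The plan also pairs multiple imputation with a sensitivity analysis, whose form can properly be left to an SAP.
- *A reader might infer that reminders will make response differ by arm.* Keeping Connected is one of three channels to be explored. The other two can reach both arms, and email, text, post and vouchers go to all carers.

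This is also a pilot. That lowers the stakes of any single estimate, but it does not make the rule sound.

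**Conclusion.** Wrong as written, in a narrower sense than bias whenever the rule applies. Where LOCF is used, it loses a share mT of any real effect and adds (mC − mT)d. Under the assumed 25% v 40% missingness, a true 0.24 SD is reported as 0.135 to 0.225, and a null drifts by at most 0.045 SD for trends within ±0.3 SD. This is attenuation and modest distortion, not reversal. The sizes rest on assumed arm-specific missingness and trend and, for the formula, on missingness that is random within arm. They apply to the primary outcome only if the WEMWBS guidance does not displace LOCF.

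The choosing test detects a 10-point gap about half the time before clustering. When it misses, the unadjusted model was biased by about −0.04 to −0.06 SD in simulation if missingness depended on baseline or endline wellbeing.

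Two faults need no assumptions: LOCF cannot be carried out where no baseline exists, and observed data cannot establish MNAR. The reminder channel is minor. Keeping Connected groups follow Level 1 WRAP, so apart from the assumed 2% control contamination they reach only the intervention arm.

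**What to change.** - Delete LOCF and the test-then-choose rule.
- State one approach in advance: a baseline-adjusted model allowing for household clustering, with multiple imputation by arm or an equivalent likelihood analysis, under missing at random. For outcomes without a baseline, use the other available covariates.
- Build the imputation model from baseline scores and whatever covariates are available. Full carer covariates cannot be assumed: the covariate list allows unknown values, and Annex 3 has no carer date of birth, which comes from the survey.
- Add a delta-based sensitivity analysis by arm. The adjusted analysis is not immune to MNAR.
- State that the WEMWBS guidance governs missing items, and reconcile it explicitly with whole-survey non-response.
- Drop the MCAR/MAR/MNAR decision table and single mean imputation of covariates.
- Send identical endline reminders to both arms, and do not use Keeping Connected groups for them.

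Cost: plan wording, a few hours of coding and one optional reminder channel.
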